5.2 Enrollment and Follow up Procedures

Up to 72 evaluable HIV uninfected participants (54 non pregnant and 18 pregnant cisgender women) will be enrolled and followed up for 16 weeks: 8 weeks with DOT PrEP, and up to 8 weeks for post drug kinetics sampling – one visit in week 9 and an additional visit within weeks 10 to 16 (i.e. 2 visits in total). Enrollment must occur within 30-day screening window. An eligible participant who is unable to schedule a study entry visit within the 30-day screening window must be re-screened prior to entry into the study. All enrolments will be scheduled on specific days to avoid confusion in implementing the proposed dosing and sampling scheme. Study entry visit (enrollment) through week 8 visit will include an adverse effect questionnaire along with medical and medication review. Safety labs and vitals can be ordered as needed at any visit.

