5.2.1 Dosing schedule and assessment of compliance

The design of the study is guided by the ~17 day half-life of TFV-DP in DBS, including 8 weeks of dosing to achieve approximately 90% of steady-state, weekly sampling at convenience times (i.e., rather than troughs), and three dosing groups (2, 4, and 7 doses per week) to demonstrate dose-proportionality. All cisgender women will be followed for 8 weeks with DOT PrEP to establish steady state in DBS and WB, and up to 8 weeks for two post-DOT PrEP sampling visits. We have chosen a dosing frequency scheme for non-daily doses to directly replicate the STRAND DOT study schedule based on the ~17 day half-life of TFV-DP in DBS: The 2 doses per week will be taken on Monday and Tuesday, and the 4 doses per week on Monday, Tuesday, Thursday, and Friday. This schedule will permit simultaneous evaluation of concentrations derived from intermittent and day-by-day dosing. The operationalization of specific days for dose taking can be adjusted prior to study start while maintaining the randomized adherence patterns (frequency of dosing taking) to permit efficient study operations and to minimize the burden on study participants. This is possible due to TFV-DP long half-life and planned sampling at steady state. Therefore, any chosen days would still be appropriate.

All doses will be witnessed, as described above, in person by a study personnel in private room at the Thika clinic or other predetermined location to maximize convenience for the participant. On dosing visits, the participant will take the dose by mouth and study personnel will ensure the tablet is swallowed by

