7.3 Data Analysis

7.3.1 Primary outcomes

Primary outcome 1: The goal is to quantify the effect of dose on steady state TFV-DP in DBS and PBMC based on an incomplete block design. C_{ss} (drug concentration at steady state) will likely require a normalizing log transform, such that geometric means and CIs will be reported. Dose proportionality will be assessed using the power model (on the natural log scale) $\ln(Y_{ijk}) = \mu + S_i + \beta \log(D_k) + \varepsilon_{ijk}$ (Eqn. 1).⁷³ Where Y_{ijk} is the response, C_{ss}, for the kth dose (k=2, 4, and 7 doses per week), ith subject (i=1...54); μ is the overall mean, S_i is a random subject effect, and ε_{ijk} is random error. Dose proportionality dictates that $\beta=1$ for dose-dependent parameters and we will assume dose proportionality if the 90% CI is contained within the limits (0.8, 1.25). We will use the observed week 8 concentrations for the dose-proportionality model. Week 8 is approximately 90% of steady state (3.3×17 -day half-life = 8 weeks). The SAS

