mixed procedure will be utilized for model (Eqn 1), again assuming a random subject effect. For the primary analysis, we assume no effect of ‘non-daily dosing’ regimens; although this will be examined in a secondary analysis. If dose proportionality is not shown, we will examine proportionality separately for each of the “non-daily dosing” dosing regimens. If dose proportionality is still not demonstrated when adherence regimens are examined separately, we will consider dose as a categorical predictor. Change in objective function and/or AIC will be used to compare models. This approach will be used to further probe dose proportionality and the final model(s) will be used as a basis for simulation studies. Additionally, we will fit a model with following first-order kinetic equation to the TFV-DP data: $C_t = C_{ss} * (1 - e^{-k*t})$, where C_t is the TFV-DP at time t (i.e., day 4, weeks 1, 2, 3, 4, 5, 6, 7, 8), C_{ss} is the fitted concentration at the steady-state plateau and k is the fitted elimination rate constant, and half-life is $\ln(2)/k$. The fitted C_{ss} will be used in the dose-proportionality model. These approaches use non-compartmental and a simple one-compartment model, respectively. Finally, the percentage of dose can be used as a regressor because the concentration at steady-state is directly proportional to dose frequency and TFV-DP clearance [$C_{ss} = (\text{dose rate})/CL$]. Time post dose does not have to be accounted for because it does not impact the TFV-DP concentration given the 17-day half-life. Importantly, we have used these approaches to assess dose proportionality in two similarly designed studies that have been published. [<https://pubmed.ncbi.nlm.nih.gov/32539288/>].⁷⁴⁻⁷⁸

Primary outcome 2: The goal is to identify TFV-DP cut points associated with adherence levels. For the primary analyses, we will attempt to discriminate adherence for 2, 4 and 7 dosing based upon TFV-DP. As above, we will combine the “non-daily dosing” regimens. Linear mixed models with random intercepts, 25th percentiles, and receiver operating characteristics curves will be used to generate predicted concentration thresholds for varying dosing frequency (ranging from 2 to 7 doses/week) for each matrix-analyte pair. Analyses will be adjusted for age, contraception use, study arm, BMI, eGFR, and hematocrit.

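### The fit that yields Css and half-life uses only the rising curve to week 8; the two post-DOT samples drawn for washout kinetics have no stated analysis

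*Combined protocol and SAP*

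**What the plan says.** Section 7.3.1 gives the power model for dose proportionality two responses. The first is observed: "We will use the observed week 8 concentrations for the dose-proportionality model", with the remark that "Week 8 is approximately 90% of steady state". The second comes from a first-order accumulation equation, C_t = Css(1 - e^(-kt)). Its data are listed explicitly: "where C_t is the TFV-DP at time t (i.e., day 4, weeks 1, 2, 3, 4, 5, 6, 7, 8". In that fit k "is the fitted elimination rate constant, and half-life is" ln(2)/k, and the fitted Css "will be used in the dose-proportionality model" as well.

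Section 5.2.1 takes a half-life of about 17 days for TFV-DP in DBS as its basis and plans "8 weeks of dosing to achieve approximately 90% of steady-state".

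Section 5.2 then schedules "up to 8 weeks for post drug kinetics sampling", as two visits. Section 5.2.2 places the first in week 9, at least 48 hours after the last dose, and the second in weeks 10-16. Both collect plasma, whole blood, DBS and PBMC. Section 9.1 repeats the post-drug kinetic purpose. Neither Section 7.2 nor Section 7.3 mentions these samples.

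**The concern.** A rising curve that has not reached its plateau separates plateau from rate poorly: a higher Css with a slower k gives nearly the same nine points as a lower Css with a faster k. A sample taken after dosing stops moves the other way with k, so it breaks that trade-off. The trial collects such samples and states no use for them.

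Two things depend on the fit. One is the half-life in these women. Section 1.2.2 argues that their pharmacology may differ from that of US populations, so 17 days is a planning value here. The other is the step from a week-8 reading to a steady-state reading. Section 2.1 expects women's thresholds to differ from those of MSM. A week-8 DBS value set beside a steady-state figure is low for a reason unrelated to sex or population, namely incomplete accumulation.

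**Working it through.** **The plan's own figure.** With a 17-day half-life, k = ln(2)/17 = 0.0408 per day. At day 56, 56/17 = 3.29 half-lives, and 1 - 2^(-56/17) = 0.898. The stated 90% is reproduced, as is Section 7.4's week-8 mean: 0.90 x 1605 = 1444.5, stated as 1445. For half-lives of 14, 17 and 20 days the week-8 fraction is 0.938, 0.898 and 0.856.

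**Inputs for precision.** Planned times are days 4, 7, 14, 21, 28, 35, 42, 49 and 56 (Section 7.3.1). Added times are day 59, an early week-9 visit, and day 84, inside the weeks 10-16 window. Residual error is not given in the documents. I assume 15% proportional error, or alternatively 100 fmol/punch additive error with Css = 1605.

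**Model.** Up to the last dose time T, C = Css(1 - e^(-kt)). Afterwards, C = Css(1 - e^(-kT))e^(-k(t-T)). The sensitivity of ln C to ln Css is 1 throughout. Its sensitivity to ln k is

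- on treatment: kt e^(-kt)/(1 - e^(-kt)), which is 0.92 at day 4 and 0.26 at day 56;
- after T = 56: 0.26 - k(t - 56), which is 0.14 at day 59 and 0.26 - 1.14 = -0.88 at day 84.

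The change of sign is where the new information comes from.

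**One woman's fit** (standard errors from the inverse of the expected information matrix):

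| Assumed error | Parameter | Planned 9 samples | Plus days 59 and 84 | Reduction |
|---|---|---|---|---|
| 15% proportional | ln Css | 0.135 | 0.059 | 56% |
| 15% proportional | ln k | 0.222 | 0.096 | 57% |
| 100 fmol/punch additive | ln Css | 0.093 | 0.052 | 44% |
| 100 fmol/punch additive | ln k | 0.208 | 0.122 | 42% |

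With the late sample at day 70 or day 112 instead, the reductions are 45% or 64% for ln Css and 40% or 74% for ln k under proportional error. Under additive error they are 45% or 33%, and 40% or 30%. The proportional-error percentages do not depend on the 15%: they are the same at 10% and 20%.

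**One arm's mean (n = 18).** The SE of mean ln Css is sqrt((w² + s²)/18), where s is the single-woman SE and w the between-woman SD. Section 7.4's CV of 25.2% gives a log-scale SD of sqrt(ln(1 + 0.252²)) = 0.248.

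- Taking w = 0.248: sqrt((0.0616 + 0.0183)/18) = 0.067 falls to sqrt((0.0616 + 0.0035)/18) = 0.060, about 10%.
- Removing the assumed residual error first, w² = 0.0616 - 0.0225 = 0.0391: 0.056 falls to 0.049, about 14%.

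For ln k with an assumed 15% between-woman spread, sqrt((0.222² + 0.15²)/18) = 0.063 falls to sqrt((0.096² + 0.15²)/18) = 0.042, about a third.

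**Effect on the slope.** If every arm is at the same fraction f of its plateau, ln(f x dose) = ln f + ln(dose). The constant goes into the intercept and beta stays at 1.000. Beta moves only if half-life differs by arm: 14, 17 and 20 days for 2, 4 and 7 doses gives 0.928, and the reverse order gives 1.072.

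**The case against.** Much of the case on the other side stands.

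- **The shortfall is disclosed and partly handled.** The plan states the 90% in Sections 5.2.1, 7.3.1 and 7.4, plans around 1445, and adds a fitted plateau.
- **The planned fit is adequate for a group-level correction.** The derivative of the week-8 fraction with respect to ln k is 2.283 x 0.102 = 0.233. An arm-level SE(ln k) of 0.052 (no spread in k) to 0.063 (15% spread) therefore gives an SE for the fraction of 0.012 to 0.015. That is enough to tell 86% from 94%.
- **Other models might use the samples.** Section 7.3.2 plans non-linear mixed models across matrices with no time restriction, and Section 13 mentions population PK for plasma. Neither names the post-DOT samples or says that TFV-DP decay will be estimated.
- **The ranking of the two responses is arguable.** The text gives observed week-8 values first and introduces the fit as an addition, which suggests an order without stating one.

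A reader might infer that comparing week-8 values with the MSM cut-off of 1250 would raise the share of perfectly dosed women below it from 25% to 40%. That needs 1250 to be a full-plateau 25th percentile. Section 1.2.1 calls it a 25th percentile but gives no time point. From Section 7.4's 1605 ± 405, the share would go from about 19% to 30-33%, depending on the distribution assumed. Section 7 also specifies no formal comparison with MSM values.

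**Conclusion.** The point holds as a worthwhile improvement to the kinetic analysis. It does not show a fault in the primary test. Samples drawn for washout kinetics have no stated analysis, and the stated equation cannot take them. Including them cuts one woman's standard errors for Css and k by about 56% under proportional error, or 42-44% under additive error, with the late sample at day 84. The gain is mainly in half-life and individual Css; the arm mean of ln Css improves by only about 10-14%.

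Two stronger readings are not supported. One is that dose proportionality on week-8 values is biased: a common shortfall cancels. The other is that fitted Css must replace the observed value as the primary benchmark: that is a matter of choice, since the observed value needs no extrapolation and only has to be labelled correctly.

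The figures rest on an assumed residual error, a 17-day half-life and equal k in both phases. The 17 days and 90% are DBS values; the documents give no PBMC half-life, so neither carries over to PBMC.

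**What to change.** In Section 7.3.1:

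1. Fit one non-linear mixed model to all samples: Css(1 - e^(-kt)) to the actual last-dose time T, then Css(1 - e^(-kT))e^(-k(t-T)), with random effects on ln Css and ln k. Use actual sample times, since the last visit can fall anywhere in weeks 10-16.
2. Exclude post-DOT samples from women who continue PrEP.
3. Check equality of k by fitting separate accumulation and washout rates. If they differ, report both.
4. State which response is primary for dose proportionality. Observed week-8 values may stay.
5. Label week-8 DBS benchmarks as about 90% of steady state, with the 94%, 90% and 86% range for half-lives of 14, 17 and 20 days. Use the fitted Css when setting DBS values beside steady-state MSM figures.

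The cost is SAP wording and modest modelling, with no new samples. Section 7.6 has concentrations batch-tested at the end of primary data collection, so the change can be fixed before results exist.

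The limits should be written down too. The pregnant cohort will supply little washout data: the Table 5 footnote ends their blood work at week 9, and Section 5.4 offers post-DOT visits only to those who stop PrEP. Their Css will therefore rest mostly on accumulation data, which should be said wherever the two cohorts are compared.

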asking the participant to show that their mouth is empty. Flexible clinic scheduling will be available to promote high rates of follow-up and compliance and minimize participant's burden. Where dosing cannot be witnessed in person, dosing will be witnessed by video communication via WhatsApp, Zoom, FaceTime, Skype, or other video-streaming device that is agreed upon by the participant and study personnel will be used. Only cisgender women with an active smart phone will be enrolled in this pharmacological study to permit offsite observation of dose taking for the required DOT PrEP. Participants will be supported with commensurate data/internet bundles. A one-month supply of back-up medication will be provided to participants at study enrollment to be used if participant is unable to complete visit at the clinic. All these doses taken offsite will still be directly observed by study staff by live video streaming and participants will be asked to open their mouth afterwards to confirm swallowing. Dosing may occur at variable times within the assigned dosing day. All doses will be taken without regard to food, but meal information will be collected with each dosing event.

Study personnel will use a dosing log to document directly observed doses. Participants will be given a detailed calendar that shows scheduled dosing days. This schedule will also be reinforced when study personnel interact with participants.

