5.2.2 Protocol pharmacology sampling visit schedule

On protocol-specified clinic visits (described below and Table 5), a blood sample will be collected from an arm vein for plasma/WB/RBC/DBS/PBMC isolation and safety laboratories. Hair will be cut from the scalp for comparison with other drug measures. Adverse events will be assessed. All protocol-specified clinic visits are detailed below. Each protocol-specified clinic visit will have a window of up to three days for sample collection (up to a week for hair).

Clinic visit 1: Study entry visit (must be within 30 days after screening visit)

- Medical, sexual, contraception, antenatal and vaccine history review
- Obtain study blood work: WB, DBS, PBMC, plasma, (pre-drug for endogenous molecules such as nucleosides)
- Urine β HCG
- Study urine: (baseline endogenous molecules such as nucleosides)
- STI tests (CT, GT, syphilis)
- hDNA
- Vaginal swab
- Dispense back up PrEP medication: subject home supply
- Dispense study dosing calendar
- DOT: Witness first PrEP dose

Clinic visit 2: Week 1 Dose 4 visit (for 2 doses per week group this will be 4 days since first dose:

- Study Bloodwork: WB, DBS, PBMC, plasma
- Study urine
- Finger stick for DBS
- Cervicovaginal biopsy: Random **subset (50%) of non-pregnant cohort only**
- Vaginal swab
- Medical, sexual, contraception, antenatal and vaccine history review
- AE assessment
- Concomitant Medication Review
- DOT

Clinic visit 3: Week 1 (Dose 7) visit:

- Study bloodwork: WB, DBS, PBMC, plasma
- Study urine
- Finger stick for DBS
- Vaginal biopsy: **Random subject (50%) of non-pregnant cohort only**
- Vaginal swab
- Blood work: hDNA for those who consent to drug transport gene testing.
- Medical, sexual, contraception, antenatal and vaccine history review
- AE assessment
- Concomitant Medication Review
- DOT

Clinic visit 4: Week 2 (Dose 14) visit:

- Study bloodwork: WB, DBS, PBMC, plasma
- Study urine
- Medical, sexual, contraception, antenatal and vaccine history review
- AE assessment
- Concomitant Medication Review
- DOT

Clinic visit 5: Week 3 (Dose 21) visit:

- Study bloodwork: WB, DBS, PBMC, plasma
- Study urine
- Medical, sexual, contraception, antenatal and vaccine history review
- AE assessment
- Concomitant Medication Review
- DOT

Clinic visit 6: Week 4 (Dose 28) visit:

- HIV rapid test
- Urine β HCG
- Study bloodwork: WB, DBS, PBMC, plasma
- Study urine
- Vaginal biopsy: **Non-pregnant cohort only**
- Vaginal swab
- Hair collection

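### The accumulation curve assumes evenly spread dosing, so in the clustered 2- and 4-dose arms it distorts the fitted half-life and can bias the fitted Css by arm

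*Combined protocol and SAP*

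**What the plan says.** Section 7.3.1 (Primary outcome 1) gives two routes to dose proportionality. The first puts observed week-8 concentrations into the power model. The second, introduced as an addition, fits Ct = Css(1 − e^(−kt)), where Ct "is the TFV-DP at time t (i.e., day 4, weeks 1, 2, 3, 4, 5, 6, 7, 8", takes half-life as ln(2)/k, and uses the fitted Css as the response. For the power model, "we will assume dose proportionality if the 90% CI is contained within the limits (0.8, 1.25". The same section says that time since the last dose can be ignored because of the 17-day half-life.

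Section 5.2.1 sets the dosing days: "The 2 doses per week will be taken on Monday and Tuesday, and the 4 doses per week on Monday, Tuesday, Thursday, and Friday". Section 5.2.2 places the first on-treatment sample at day 4; "for 2 doses per week group this will be 4 days since first dose". Section 5.2.1 also says "Study personnel will use a dosing log to document directly observed doses".

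The plan does not state the error model for the curve, or whether k is per woman, per arm or common. It does not say that actual dose dates enter the fit.

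**The concern.** The equation describes constant-rate input from time 0. That suits the daily arm. Four days after the first dose, the 2-dose arm has taken 2 doses, where even input implies 2 × 4/7 = 1.14. The 4-dose arm has taken 3 (4 if sampled after that day's dose), against 4 × 4/7 = 2.29. The daily arm has taken 4, against 4.

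The early sample therefore lies above the curve in the non-daily arms only, and a free k rises to meet it. The misfit follows the arm, which is the contrast being estimated. The trial could report TFV-DP elimination that varies with dosing frequency when it does not, and could shift the slope in the fitted-Css analysis. Section 7.3.2 reuses the Aim 1 PK models to simulate other regimens, so the error could carry into those cut points.

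**Working it through.** **Inputs from the documents.** Half-life about 17 days ("The design of the study is guided by the ~17 day half-life of TFV-DP in DBS", Section 5.2.1); dosing and sampling days as above; 18 women per arm, CV 25.2% and 10% non-completion, about 16 per arm (Section 7.4); limits 0.8 to 1.25 (Section 7.3.1).

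**Assumptions not in the documents.** Instantaneous TFV-DP input, exact dose proportionality, and in the simulations a residual CV of 10% and a CV of k of 10%.

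**The plan's own figure.** "Week 8 is approximately 90% of steady state". 1 − 2^(−56/17) = 0.898, and 3.3 × 17/7 = 8.0 weeks. This reproduces.

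**Day 4, just before any dose that day.** k = ln 2/17 = 0.0408 per day. With each dose adding one unit, the concentration is the sum of e^(−k(4 − t_j)) over doses taken at times t_j. The even-input curve is (doses per week/7)/k × (1 − e^(−4k)).
- 2-dose: 0.850 + 0.885 = 1.734, against 1.055. Ratio 1.64.
- 4-dose: 2.694 against 2.109. Ratio 1.28.
- Daily: 3.616 against 3.691. Ratio 0.98.

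**Week 8, just before the next dose.** The same ratios are 0.88, 0.94 and 0.98. The 2-dose arm is then 6 days past its last dose, and 2^(−6/17) = 0.78, a fall of about 22%. Regressing the log of these concentrations on log dose gives a slope of 1.084 with no curve fitted at all.

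**Noise-free fits at days 4, 7, 14, …, 56, with k free in each arm:**

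| Fit | Half-life, 2/4/7 doses (days) | Css ÷ true average Css | Slope |
|---|---|---|---|
| Log scale | 10.6 / 13.5 / 17.0 | 0.75 / 0.86 / 0.98 | 1.21 |
| Unweighted | 15.2 / 16.2 / 17.0 | 0.85 / 0.92 / 0.98 | 1.12 |
| Either, day 4 omitted | 17.0 / 17.0 / 17.0 | 0.88 / 0.94 / 0.98 | 1.08 |

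At nominal days the early sample causes the half-life artefact. It adds about 0.13 (log scale) or 0.03 (unweighted) to a slope error already present at week 8.

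**One k common to all arms.** Half-life can no longer differ by arm. The slope is 1.03 to 1.08 at nominal days, but 0.83 to 0.89 if weekly samples come 1.5 days late.

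**How often the 90% CI rule is met under exact proportionality** (k fitted per woman, 1,500 simulated trials; the last row used 150):

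| Setting | 18 per arm | 16 per arm |
|---|---|---|
| Log scale, nominal days | 12–28% | 12–27% |
| Unweighted, nominal days | 53–58% | 49–53% |
| Weekly samples 0 to +3 days late | 80% (log), 86% (unweighted) | 75%, 82% |
| Samples ±3 days | 55% (log), 75% (unweighted) | 51%, 69% |
| Observed week 8, nominal days | 75–76% | 69–70% |
| Same curve, truly even dosing | 86% (log), 81% (unweighted) | 80%, 74% |
| Fit using actual dose dates | 80–88% | not run |

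The ranges at nominal days cover two readings of the visit day. Over residual CVs of 5 to 15%, the unweighted rate at nominal days (18 per arm) runs from 40 to 64%.

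The half-life pattern persists when samples spread. With samples 0 to +3 days late, the median fitted half-lives are 8.7/11.9/15.7 days (log scale) and 9.1/12.5/14.6 days (unweighted). The fit using actual dose dates returns 16.9 to 17.0 days in every arm and a slope of 0.99 to 1.00.

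**The case against.** A reader might infer that the trial would usually miss proportionality even if it were exact. The documents do not support that. It holds only for a log-scale fit with k per woman and samples on the nominal days. Section 7.3.1 states neither an error model nor a structure for k, and its log transform concerns Css in the power model. Sections 5.2.3.1 and 9.1 set no timing of samples relative to doses, and a 3-day window applies. Unweighted fits pass in about half of trials, and most trials pass when weekly samples fall 0 to 3 days late.

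Nor can one say that Css is always too low at low dosing frequency, because the direction turns with sampling day. Day 4 is not the sole cause either. Section 5.2.1 also lets the dosing days change before the study starts; in one more widely spaced pattern tried as a sensitivity check, the slope was still 1.08 to 1.20 at nominal days.

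On impact, observed week 8 is the first-stated response for proportionality and does not depend on the curve. Primary outcome 2 is not described as using the fitted Css. The plan also has a secondary look at non-daily dosing and a categorical-dose fallback.

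All of this limits the reach of the point. None of it repairs k, and no section puts actual dose times into the curve.

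**Conclusion.** The point stands in limited form and should be fixed. Followed exactly, with k free per woman or arm, the stated equation gives a half-life that rises with dosing frequency when true elimination is the same. This held in every Monday/Tuesday timing and weighting variant tried at 17 days. The bias in fitted Css is real at nominal days, but its size and sign depend on choices the plan leaves open. Those choices alone move the pass rate from about 12% to 86% (18 per arm) with identical biology.

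The figures rest on instantaneous input, a 17-day half-life in DBS and the assumed residual and k variability. PBMC is also a primary matrix, and the documents give no half-life for it. Over an assumed 2 to 10 days, the fitted slope ran from about 1.2 to 1.8 just before the next dose, and from about 0.5 to 0.94 with samples 1.5 days late. The problem could be larger there.

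**What to change.** In Section 7.3.1, replace the curve with superposition over the logged directly observed doses, using actual dose and sample times: C(t) = a × Σ e^(−k(t − t_j)), summed over doses taken before t. Derive average Css = a × (doses per week/7)/k and use it in the dose-proportionality model. Pre-specify the error model and whether k is common or subject-specific. Amend the statement that time since dose can be ignored, since the 2-dose arm falls by about 22% over 6 days at the plan's own half-life.

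Dropping day 4 from the non-daily arms is not an adequate substitute. It restores the half-life only at nominal sampling days and leaves the slope at about 1.08.

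The cost is SAP wording and modest non-linear model code. The dosing log supplies the dose dates, so no new data, visits or dosing changes are needed.

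### The threshold analysis for primary outcome 2 names no visit and has no time-on-drug term; if the on-drug samples are pooled, the DBS benchmarks fall well below week 8 and steady state in all three arms

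*Combined protocol and SAP*

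**What the plan says.** All references are to the combined protocol and SAP. For primary outcome 2, section 7.3.1 states: "Linear mixed models with random intercepts, 25th percentiles, and receiver operating characteristics curves will be used to generate predicted concentration thresholds". These are to cover 2 to 7 doses per week and every matrix-analyte pair. The adjustment set follows: "Analyses will be adjusted for age, contraception use, study arm, BMI, eGFR, and hematocrit". Neither sentence names a visit, a week or time on drug.

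Primary outcome 1, in the same section, is explicit about time: "We will use the observed week 8 concentrations for the dose-proportionality model". It adds that "Week 8 is approximately 90% of steady state". It also fits a first-order accumulation curve in which "C_t is the TFV-DP at time t (i.e., day 4, weeks 1, 2, 3, 4, 5, 6, 7, 8" and the plateau is Css; the fitted Css is then assigned to the dose-proportionality model. Outcome 2 refers back to this text only for combining the non-daily regimens.

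Section 5.2.1 gives the kinetics: "The design of the study is guided by the ~17 day half-life of TFV-DP in DBS". It too puts the end of the dosing period at roughly nine tenths of the plateau, and it has samples drawn every week without fixed timing after a dose.

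**The concern.** TFV-DP in DBS accumulates throughout the 8 weeks of dosing. A random-intercept model with dose and baseline covariates but no week term treats that common rise as noise around an average level, and the average lies below the week-8 level. Pooled 25th percentiles and ROC curves suffer more, because the early samples fill the lower tail of each arm.

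The cut points are a primary product. They are meant to fill the empty column beside the US values of 350, 700 and 1250 fmol/punch (section 1.2.1) and to be applied to archived Partners PrEP samples (protocol schema). The overall hypothesis (section 2.1) is that thresholds in women differ from those in MSM. Pooling the accumulation phase would produce such a difference even in women whose pharmacology matched the US reference. Even between two defensible time points, the choice can move the daily 25th percentile from one side of 1250 to the other.

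**Working it through.** **Inputs from the document.** Half-life 17 days (5.2.1). First-order accumulation equation and nine on-drug times (7.3.1). Daily-dosing mean 1605, SD 405, CV 25.2%, and 1445 at week 8 (7.4). As section 7.4 does, I take 1605 as the plateau.

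**1. Reproduce the plan's figure.** f(t) = C_t/Css = 1 − exp(−ln2 × t/17). At day 56, 56/17 = 3.29 half-lives and f = 0.898. Also 0.90 × 1605 = 1444.5. The plan's 90% and 1445 both reproduce.

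**2. Fraction of steady state at each on-drug sample.**

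| Day 4 | Wk 1 | Wk 2 | Wk 3 | Wk 4 | Wk 5 | Wk 6 | Wk 7 | Wk 8 |
|---|---|---|---|---|---|---|---|---|
| 0.150 | 0.248 | 0.435 | 0.575 | 0.681 | 0.760 | 0.820 | 0.864 | 0.898 |

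**3. Level estimated with no week term.** With balanced visits, the arm mean is the average of these fractions times Css: the arithmetic mean on the raw scale, the geometric mean on the log scale. Outcome 2 does not state a scale, so both are shown.

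- All nine visits: arithmetic mean 0.604, geometric mean 0.526.
- Against Css: 1 − 0.604 = 39.6% and 1 − 0.526 = 47.4% too low.
- Against week 8: 1 − 0.604/0.898 = 32.8% and 1 − 0.526/0.898 = 41.4% too low.

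A simulated random-intercept model without week (18 women per arm; assumed log-scale SD 0.22 between and 0.12 within women) gave 33.0% and 41.6% below week 8.

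**4. Dependence on which visits enter (DBS mean).**

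| Visits used | Below week 8 | Below Css |
|---|---|---|
| Day 4 and weeks 1–8 | 33–41% | 40–47% |
| Weeks 1–8 | 26–32% | 34–39% |
| Weeks 4–8 | 10–11% | 20% |
| Weeks 6–8 | 4% | 14% |
| Week 8 only | 0% | 10% |

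Varying the half-life from 14 to 20 days with all nine visits gives 34–44% (raw) or 42–52% (log) below Css.

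**5. Daily-dosing 25th percentile** (CV 25.2%, normal or lognormal between women, no within-woman noise): fitted Css about 1317–1331; week 8 about 1182–1195; nine visits pooled about 548–576. The pooled value is 51–54% below week 8 and 56–59% below Css. The Css and week-8 values lie on opposite sides of 1250.

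**6. ROC step, 4 against 7 doses** (dose-proportional arms; assumed within-woman log SD 0.10–0.20). Pooling lowers the AUC from 0.89–0.93 to 0.74–0.75, and the Youden cut point from about 1045–1070 to about 840–890.

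**7. Scope.** Under first-order kinetics f(t) does not depend on dose, so the proportional shift in means is the same in all three arms. The half-life is given for DBS only. For another matrix, an assumed half-life of 2 to 7 days would give a pooled shortfall in the mean of about 4–19%.

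**The case against.** The strongest reply is that pooling is inferred and nowhere stated. Equation 1 in section 7.3.1 also carries a random subject effect, yet it uses one week-8 value per woman, so the authors use this wording where only one time point enters. The serial samples already have a stated use in the accumulation curve. The precision calculation in 7.4 is built on the week-8 mean, and 5.2.1 says of the choice of dosing days: "This is possible due to TFV-DP long half-life and planned sampling at steady state". Week 8 or fitted Css is therefore a plausible intention for outcome 2.

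Much of this stands. A reader might infer that the plan does average the accumulation phase and that the cut points will come out 40–50% too low. The text does not support that as fact, because it names no visits. A reader might also infer that the model is wrong on either reading. That goes too far: with week 8 alone, a subject effect that cannot be separated from residual error is untidy but does not bias the arm means. For DBS, the paired venous and fingerstick samples at week 8 could even make it estimable. Nor is the shift peculiar to daily dosing.

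The reply does not close the gap. The week-8 and Css rules are limited by their own words to the dose-proportionality model. The steady-state remark defends the choice of dosing days and cannot describe a schedule that samples from day 4. The fingerstick duplicate exists only for DBS, whereas random intercepts are specified for every matrix-analyte pair. Applied literally, the text leads an analyst to enter several visits per woman with no time term.

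**Conclusion.** The point holds as a conditional one. The threshold analysis omits both the visit and any time-on-drug term, and its random intercepts point towards repeated samples. If day 4 to week 8 samples enter, DBS mean benchmarks in all arms would be about 33–41% below week 8 (40–47% below steady state), and pooled 25th percentiles about 51–54% below week 8. Using weeks 4–8 shrinks the shortfall in the mean to 10–11% against week 8. Using week 8 alone removes it, but the values remain about 10% below steady state.

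These sizes rest on the plan's first-order model, its 17-day half-life and complete, balanced visits; the percentiles also rest on its 25.2% CV. They must not be carried to PBMC, plasma or tissue, for which the documents give no half-life. Since a primary result depends on the unstated choice, it should be fixed before concentrations are seen.

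**What to change.** In section 7.3.1, primary outcome 2, state one of the following.

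- **One value per woman.** Derive benchmark means, 25th percentiles and ROC cut points from each woman's fitted Css, using the accumulation model already planned, or from her week-8 sample labelled as about 90% of steady state. A random intercept is then not needed.
- **Serial samples.** Add week as a categorical fixed effect with a week-by-dose interaction, keep the random intercept, and read every threshold at week 8 or at Css.

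In either case, do not pool weeks in the percentile or ROC step. Use fitted Css when comparing with 350/700/1250, since section 7.4 gives its US reference value as a steady-state figure.

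The change takes a few sentences and no new data. Section 7.6 has samples tested in batches after primary data collection, so the choice can be fixed before results exist. Week 8 alone gives up some within-woman precision. Fitted Css adds some dependence on the first-order model, so reporting the week-8 values beside it would be a sensible check.
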